For categorical measures, summary statistics will include sample size, frequency, and percentages. Fisher's exact test or logistic regression will be used for treatment comparisons, unless otherwise stated. For laboratory values, both conventional (CN) and System International (SI) units will be presented. Therefore, both % and mmol/mol will be presented for HbA1c and both mg/dL and mmol/L will be presented for glucose measurements.

In this study, the negative binomial regression will be used to analyze the number of hypoglycemic episodes. Group Mean instead of LS mean will be estimated and delta method will be used to estimate the standard error of the Group Mean (Qu and Luo 2015). Group Mean is defined as the mean response in the treatment group for the studied population. The difference between LS mean and the Group Mean is that LS mean estimates the response by taking the

inverse link function on mean covariates, while the Group Mean takes the inverse link function on individual patient covariates first and then averages over all patients. For Level 2 hypoglycemia and severe hypoglycemia, the empirical method based on exposure adjusted rate (calculated by total number of events divided by total exposure) may be used for the treatment comparison if the number of episodes is too small and leads to convergency issues in the negative binomial regression model.

Below table describes the definition of baseline and post-baseline observations for different analyses.

Analysis	Baseline Observations	Post-Baseline Observations
HbA1c (treatment regimen estimand)	The baseline is the last non-missing assessment prior to or at the first day of study treatment.	Planned measurements at Visit 24 (secondary endpoint, Week 26) and Visit 31 (primary endpoint, Week 52) in EAS1. Use unplanned measurements if no planned measurement. Multiple imputation approach will be used to impute missing observations at Visit 24 (Week 26) and Visit 31 (Week 52).
HbA1c (efficacy estimand)	The baseline is the last non-missing assessment prior to or at the first day of study treatment.	Visit 5, 7, 15, 17, 24, 27, and 31 (Weeks 2, 4, 12, 16, 26, 36, and 52) in EAS2 for MMRM. Planned measurements at scheduled visits will be included. Use unplanned measurements if no planned measurements.

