Analysis model	Each endpoint will be analyzed using a logistic regression model including treatment, strata (country, GLP-1 RA treatment at randomization and SU use at randomization), and baseline HbA1c value. The odds ratio between LY3209590 and insulin degludec will be used for treatment comparison. Multiple imputation will be performed, and the statistical inference will be based on the multiple imputation framework by Rubin (1987)
----------------	---

Abbreviations: EAS1 = Efficacy Analysis Set 1; GLP-1 RA = glucagon-like peptide-1 receptor agonist;

HbA1c = glycated hemoglobin; SU = sulfonylurea.

4.5.3. **Tertiary Safety Endpoints**

For tertiary safety measures, the details are provided in Section 4.6 and the following subsections.

4.6. **Safety Analyses**

Safety measures include treatment exposure, adverse events (AE), vital signs, weight, hypoglycemia, laboratory measures and immunogenicity. All safety analyses will be based on the SS. Unless otherwise specified, safety analysis period will include both treatment period and follow-up period.

Percentages will be calculated using the safety population as the denominator. For events that are gender-specific, the denominator and computation of the percentage will include only participants from the given sex. Unless otherwise noted, Fisher's exact test will be used for treatment comparison, risk difference and 95% confidence intervals will be provided.

For continuous safety variables (for example, laboratory measures, vital signs, and weight), descriptive statistics for the observed values and change from baseline at scheduled visits during the treatment and follow-up period will be provided. For selected laboratory measures (i.e. liver enzyme tests, lipid measures), observed values, change from baseline and percentage change from baseline will be analyzed for the log-transformed values by the MMRM model using treatment, visit, and treatment by visit as fixed effect, baseline of the dependent variable as a covariate, and compound symmetry as the variance-covariance structure.

The incidence and event rate of participant-reported and CGM-based hypoglycemia will be summarized by treatment and analysis period for different types of hypoglycemia. Analysis details are provided in Section 4.6.3.1.

4.6.1. **Extent of Exposure**

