4.6.2.1. Safety Topics of Interest

4.6.2.1.1. *Severe Hypoglycemia*

Severe hypoglycemia is a severe event characterized by altered mental and/or physical status requiring assistance for treatment of hypoglycemia. The determination of a hypoglycemic event as an episode of severe hypoglycemia is made by the investigator based on the medical need of the participant to have required assistance and is not predicated on the report of a participant simply having received assistance. If a hypoglycemic event meets the criteria of severe hypoglycemia, the investigator must record the event as serious on the AE case report form (CRF).

A summary of severe hypoglycemia by decreasing risk difference will be provided. The incidence and event rate during the treatment period will be analyzed using the method described in Section 4.6.3.1. A listing of severe hypoglycemia events will also be provided.

4.6.2.1.2. *Persistent-Recurrence Hypoglycemia*

The potential risk of persistent-recurrent hypoglycemia (P-R hypoglycemia) will be assessed from the first dose date up to the end of the study. P-R hypoglycemia events will be identified using:

1. investigator assessment and clinical judgment to determine if repeated hypoglycemia may have contributed to a hypoglycemic event that degenerated with poor outcomes, and
2. a prespecified criteria to derive events from e-diary database by programming (see definition in [Appendix 10](#) [Section 6.10]).

Identification of P-R hypoglycemia based on investigator reporting is precipitated by a hypoglycemic event a participant or their caregiver informed as having resulted in a poor outcome. This information will trigger an e-mail alert notifying the investigator to contact the study participant, obtain more information about the specific hypoglycemic event, and provide the participant clinical guidance, if appropriate. Hypoglycemic events that trigger alerts to investigators are those participants or caregivers report in the e-Diary have required treatment with glucagon or IV glucose, resulted in coma, motor vehicle accident or other trauma, hospitalization, or emergency medical care.

Upon receiving the e-mail notification, investigator will access the e-diary database and answer the following question: *"In your clinical judgement, is this hypoglycemia event associated with repeated hypoglycemia events?"*. Investigator should select "Yes" or "No" as an answer.

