Event rate of Level 2 hypoglycemia events (events/participant/year): • All documented	Baseline, 0-6, 0-12, 0-26, 0-52, 12-26, 26-52 weeks, post-treatment period	Negative binomial regression with treatment and baseline HbA1c as covariates, log (exposure/365.25 days) as the offset in the model. If the number of events is too small to run the negative binomial regression, exposure adjusted rate calculated by total number of events divided by total exposure for individual patients will be provided and the empirical method (see Appendix 9 [Section 6.9] for details) will be used for treatment comparison.
Event rate of Level 3 hypoglycemia events (events/participant/year): • All documented	baseline, 0-26, 0-52, 26-52 weeks, post-treatment period	Negative binomial regression with treatment and baseline HbA1c as covariates, log (exposure/365.25 days) as the offset in the model. If the number of events is too small to run the negative binomial

Endpoint	Analysis Period	Statistical Method
		regression, exposure adjusted rate calculated by total number of events divided by total exposure for individual participants will be provided and the empirical method (see Appendix 9 [Section 6.9] for details) will be used for treatment comparison.
Event rate of Level 2/3 hypoglycemia events (events/participant/year): 
 • All documented • Nocturnal • Non-nocturnal 	baseline, 0-6, 0-12, 0-26, 0-52, 12-26, 26-52 weeks, post-treatment period	Negative binomial regression with treatment and baseline HbA1c as covariates, log (exposure/365.25 days) as the offset in the model. If the number of events is too small to run the negative binomial regression, exposure adjusted rate calculated by total number of events divided by total exposure for individual patients) will be provided and the empirical method (see Appendix 9 [Section 6.9] for details) will be used for treatment comparison. The plots of the mean cumulative functions (MCFs) by each treatment arm will also be created. The population mean for cumulative number of events up to time t, $M(t)$, will be estimated using a nonparametric estimation method described by Nelson (2003).
Incidence of Level 1 hypoglycemia events: 
 • All documented 	Baseline, 0-6, 0-12, 0-26, 0-52, 12-26, 26-52 weeks, post-treatment period	Logistic regression with treatment and baseline HbA1c as covariates.

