Incidence of Level 2 hypoglycemia events: 
 • All documented 	Baseline, 0-6, 0-12, 0-26, 0-52, 12-26, 26-52 weeks, post-treatment period	Logistic regression with treatment and baseline HbA1c as covariates.
Incidence of Level 3 hypoglycemia events: 
 • All documented 	Baseline, 0-26, 0-52, 26-52 weeks, post-treatment period	Logistic regression with treatment and baseline HbA1c as covariates.
Incidence of Level 2/3 hypoglycemia events: 
 • All documented 	Baseline, 0-6, 0-12, 0-26, 0-52, 12-26, 26-52 weeks, post-treatment period	Logistic regression with treatment and baseline HbA1c as covariates.

Endpoint	Analysis Period	Statistical Method

 • Nocturnal • Non-nocturnal 		
Potential persistent-recurrent hypoglycemia events 
 • identified by investigator • identified by pre-specified criteria (defined in Appendix 10 [Section 6.10]) 	Safety analysis period (see definition in Section 4.6)	The number of participants with at least one event will be summarized and compared by Fisher's exact test. The number of events will also be provided. Listings of the events will also be provided.

Abbreviations: HbA1c = hemoglobin A1c; Level 2/3 = Level 2 and Level 3 composite.

Note: The hypoglycemia yearly rate during defined period is calculated by the number of hypoglycemia within the period/number of days patient at risk within the period * 365.25. For rare events, 100-year rate will be provided. The hypoglycemia incidence during defined period indicates if the patient has at least 1 hypoglycemia events within the period (Yes/No).

Note: For treatment group comparison at baseline, baseline HbA1c is not included in the model.

A sensitivity analysis will be done for selected hypoglycemic endpoints where all hypoglycemic events are considered one hypoglycemic event until a succeeding glucose value is ≥ 70 mg/dL.

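### Level 3 (severe) hypoglycemia incidence is tested by logistic regression with no rule for an arm with zero events, where the result depends on a test statistic the SAP does not name

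*SAP*

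**What the plan says.** Incidence and rate of Level 3 hypoglycemia are tertiary safety endpoints (protocol Section 3, SAP Section 1.1). In the SAP 4.6.3.1.1 table, the row "Incidence of Level 3 hypoglycemia events" covers baseline, 0-26, 0-52 and 26-52 weeks, and the post-treatment period. Its method entry is "Logistic regression with treatment and baseline HbA1c as covariates", with nothing further. SAP 4.6.2.1.1 sends the severe-hypoglycemia safety topic to the same place: "The incidence and event rate during the treatment period will be analyzed using the method described in Section 4.6.3.1".

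The Level 3 rate row of that table does have a sparse-data rule, beginning "If the number of events is too small to run the negative binomial" and leading to the empirical method of Appendix 9. SAP 4.1 repeats that rule ("For Level 2 hypoglycemia and severe hypoglycemia, the empirical method based on exposure adjusted rate") and ties it to convergence of the negative binomial model.

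Two general rules bear on the choice of test:
- SAP 4.1 says of categorical measures: "Fisher's exact test or logistic regression will be used for treatment comparisons, unless otherwise stated". Protocol 9.3.5 also allows either test and gives no criterion.
- SAP 4.6 makes Fisher's exact test the safety default unless something else is noted. It "will be used for treatment comparison, risk difference and 95% confidence intervals will be provided".

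**The concern.** Severe events may be few, and the SAP allows for that when it analyses their rate. The incidence comparison has no such provision. If one arm has no participant with an event, treatment perfectly predicts the absence of events in that arm. The likelihood then keeps increasing as the log odds ratio goes to infinity, so there is no finite estimate, and the Wald standard error grows faster than the estimate.

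No other part of the SAP supplies a rule. The Section 4.6 default gives way to the specific table row. The Section 4.1 rule allows either test without saying when. The Appendix 9 fallback is for rates, and it would fail here too: it uses the log of the event rate and a variance containing the arm's event total to the power -2, and neither is defined when that total is zero.

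The prespecified test of severe hypoglycemia incidence could therefore come out significant or not according to an analyst's unrecorded choice of statistic, made after the counts are known.

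**Working it through.** **Sample size.** SAP Section 5 randomizes about 888 participants 1:1, so 444 per arm. Its completer figure reproduces: 444 × 0.85 = 377.4, stated as 377. Its primary power also reproduces: SE = 1.1 × √(2/377) = 0.0801, 0.4/0.0801 − 1.96 = 3.03, and Φ(3.03) = 0.9988, stated as at least 99%. The documents give no figure for Level 3 incidence; only the 444 per arm is used below.

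**Fisher's exact test, 0/444 against 6/444.** With equal arms, the two-sided p is 2 × ∏(444 − i)/(888 − i) for i = 0 to 5, which is 0.0307.

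**Logistic model on the same data.** The terms are intercept, treatment and baseline HbA1c, fitted by Newton-Raphson. Baseline HbA1c is simulated as roughly N(8.2, 0.9) limited to 7.0–10.5; the mean and SD are assumptions, and the limits are the screening range in inclusion criterion 3. Wald p-values are after 20 iterations.

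| Events, one arm (other arm 0) | Risk difference | Fisher p | Wald p | Likelihood-ratio p |
|---|---|---|---|---|
| 3 | 0.68% | 0.249 | 0.999 | 0.037 |
| 5 | 1.13% | 0.062 | 0.999 | 0.007 |
| 6 | 1.35% | 0.031 | 0.999 | 0.004 |
| 8 | 1.80% | 0.0076 | 0.998 | 0.0009 |
| 10 | 2.25% | 0.0019 | 0.998 | 0.0002 |

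The Wald value depends on when the iteration stops. For 0 against 6 it is 0.777 at 8 iterations, 0.955 at 12 and 0.999 at 20, and it approaches 1. It is never significant.

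The likelihood-ratio value can be checked without the covariate: G² = 2 × [6 ln 2 + 438 ln(438/441) + 444 ln(444/441)] = 8.36 on 1 df, p = 0.0038. With a simulated covariate it is about 0.004 to 0.005, depending on the draw.

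**The failure is specific to the zero cell.** With 1 against 10 events the Wald, likelihood-ratio and Fisher p-values are 0.028, 0.003 and 0.011. With 2 against 10 they are 0.037, 0.015 and 0.037. All are finite and below 0.05.

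**How often one arm is empty.** Let r be the 52-week risk, assumed equal in both arms, and q = (1 − r)^444. Exactly one empty arm has probability 2q(1 − q):
- r = 0.1%: q = 0.641, giving 46%
- r = 0.2%: q = 0.411, giving 48%
- r = 0.5%: q = 0.108, giving 19%
- r = 1%: q = 0.012, giving 2%

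Both arms are empty with probability q² (41%, 17%, 1.2% and about 0.01%), and then there is nothing to compare.

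**How often Fisher and Wald disagree at 0.05.** This needs 0 against 6 or more. From the binomial distribution with 444 per arm, the probability is 0.03% if both risks are 0.2%, 1.6% for 0.1% against 0.5%, 12% for 0.2% against 1%, and 18% for 0.1% against 1%.

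**The case against.** A reader might infer that the planned test must return a p-value near 1 whatever the other arm shows. The documents do not support that. The row names a model but no test statistic, and the likelihood-ratio test from that model rejects readily, with smaller p-values than Fisher's. What stands is that the choice is open: at 0 against 10 it moves p from about 0.0002 to about 1. The likelihood-ratio route still provides no finite odds ratio.

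A reader might also infer that a real imbalance could be hidden. It would not be. SAP 4.6.2.1.1 plans a summary of severe hypoglycemia by risk difference and a listing of events. Severe events must be recorded as serious, and SAP 4.6.2 tabulates serious adverse events by risk difference. This objection stands, and it limits the point to the inferential comparison.

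Nor do the documents show that an empty arm is likely. They state no expected risk, and Appendix 9 gives severe hypoglycemia in type 2 diabetes as an example of an event that is not very rare. Fisher and Wald disagree at 0.05 with appreciable probability only when the true risks differ considerably. Even so, the SAP provides for small counts in the Level 3 rate row, and the incidence row also requires comparisons over shorter periods, where counts can only be the same or lower.

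Finally, the endpoint is tertiary, and SAP 2.1 makes no multiplicity adjustment for safety assessments. This bears on priority, not on whether the method works.

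**Conclusion.** The point holds in a limited form. The stated method for Level 3 incidence has no provision for an arm without events. In that case it yields no finite odds ratio, and its p-value depends on an unnamed statistic: for 0/444 against 6/444, above 0.99 by Wald and about 0.004 to 0.005 by likelihood ratio, against 0.031 by Fisher's exact test.

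The chance that exactly one arm is empty is about 46%, 48% or 19% at equal 52-week risks of 0.1%, 0.2% or 0.5%, and about 2% at 1%. These risks are assumptions. The logistic p-values rest on a simulated HbA1c covariate, but the separation does not depend on it.

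The primary and key secondary analyses are unaffected, and so is the descriptive reporting of severe hypoglycemia. The change should be made because it is cheap and settles the comparison before the data are seen.

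**What to change.** In the SAP 4.6.3.1.1 table, for Level 3 incidence in every listed period, replace logistic regression with Fisher's exact test plus the risk difference and its 95% CI. This is already the Section 4.6 default, and the last row of the same table (persistent-recurrent hypoglycemia) already uses Fisher's exact test. Name the interval method for the risk difference, so that no similar choice stays open. The cross-reference in SAP 4.6.2.1.1 then needs no edit.

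Only SAP wording changes; no new data are needed. The comparison loses its baseline HbA1c adjustment, and Fisher's test is more conservative than the likelihood-ratio test at very low counts (0 against 5: 0.062 against 0.007). No change is proposed for the other incidence rows, because the documents give no basis for choosing a count threshold there.
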